An adverse events is defined as an unanticipated problem which meets all of the following criteria: a) unexpected (in terms of nature, severity, or frequency) given the research procedures described in protocol-related documents and the characteristics of the subject population being studied, b) related or possibly related to participation in the research and c) suggests that the research places subjects or others at a different or greater risk of harm than was previously known or recognized. A 'serious' adverse event is defined as any event in which the outcome results in any of the following: death, a life-threatening adverse drug experience, inpatient hospitalization or prolongation of existing hospitalization (for > 24 hours), a persistent or significant disability/ incapacity or substantial disruption of the ability to conduct normal life functions; a congenital anomaly or birth defect; important medical events that may not result in death, be life threatening, or require hospitalization may be considered a serious adverse drug experience when, based upon medical judgment, they may jeopardize the participant and may require medical or surgical intervention to prevent one of the outcomes listed, above. All other events will be considered 'non-serious.'

In addition to reporting any events as they occur to the IRB, a progress report and request for IRB renewal will be submitted the Northwestern University IRB annually. All non-serious adverse events will also be submitted to the RHLCCC Clinical Research office semi-annually. Furthermore, study progress reports will be submitted to the RHLCCC Clinical Research Office Data Monitoring Committee semi-annually. These reports will include accrual, withdrawals, reported adverse events and compliance issues.

9.3 *Procedures performed to lessen the probability or magnitude of risks.*

Phase 1. All participants will be informed during screening and in their informed consent with respect to how much time interviews, and/or app development will involve. All interviews and telephone/web-based app development sessions and interviews will be digitally recorded when possible; digital files will be stored on a password-secured network drive. Recordings will be transcribed verbatim and de-identified. Recordings will be destroyed at the end of the study. For intervention development, each participant will be randomly assigned an identification number to ensure confidentiality of data. All raw data will be de-identified and kept confidential.

Although, the purpose of this field test is NOT to test how well it works to increase physical activity, but rather to evaluate the app's functioning and ease of use in everyday life and participants will be explicitly told NOT to change their PA behavior and that the data they enter does not have to be accurate, we do recognize that some individuals may still attempt to increase their PA and to accurately respond to questions/prompts. Thus, we will follow the same procedures detailed, below, for Phase 2.

Electronic versions of all data will be kept on a password protected network with access limited to study investigators. Only the investigators will have access to participant data. Confidentiality will be further maintained by reporting only group level data in study publications and presentations. All staff with access to the data will have completed

PROTOCOL TITLE: Designing with Dissemination in Mind: Optimization of a mHealth Physical Activity Intervention for Breast Cancer Survivors (Fit2Thrive)

Northwestern University requirements for the responsible conduct of research including the Collaborative Institutional Training Initiative (CITI) Training Modules.

Phase 2. All participants will be informed during screening and in their informed consent with respect to how much time the program, questionnaire completion, and all testing will involve. In addition, they will also be informed of the risks associated with participating in an exercise program. Survivors and buddies will be informed that participation is completely voluntary and they can discontinue at any point. They will also be provided with the option “I prefer not to answer” for every question in the study so they can opt-out of answering any questions for which they do not want to share responses or which make them uncomfortable.

Breast cancer survivors will be provided with an exercise prescription to progress safely through the program to minimize risk (see Table 5). All participants will be able to contact study investigators at any point by phone, e-mail or messaging through the app should they have any concerns regarding participation.

Table 5. Fit2Thrive Exercise Prescription

Week	Weekly Goal (Mins)	# Sessions Per Week	Session Duration (Mins)	Session RPE	Session Target Heart Rate (% Max HR)
1	30	2-3	10-15	10-12	50-60%
2	45	2-3	15-20	10-12	50-60%
3	60	3	20	10-12	50-60%
4	75	3	25	10-12	50-60%
5	90	3	30	10-12	50-60%
6	105	3	35	10-12	50-60%
7	120	3-4	30-40	10-12	50-60%
8	135	3-4	30-45	13-15	60-75%
9	150+	3-5	30-60	13-15	60-75%
10	150+	3-5	30-60	13-15	60-75%
11	150+	3-5	30-60	13-15	60-75%
12	150+	3-5	30-60	13-15	60-75%
13-24	150+	3-5	30-60	13-15	60-75%

RPE= Rating of Perceived Exertions; HR= Heart Rate

Each participant will be randomly assigned an identification number to ensure confidentiality of data. RedCap does require an e-mail address to send the patient reported outcome measure links to participants and thus, data will be temporarily linked to individuals' e-mail addresses and first names which may be included in the e-mail for personalization purposes. However, these links will be removed when questionnaire data is downloaded and this data will then only be linked to the participant's identification number. Nitro Study Tracker, NOTIS and the study RedCap tracking database are the only places where the identification number and the participant's name will appear together in the present study and will only be accessible by the investigators.

For post-intervention interviews, all participants will be informed during screening and in their informed consent with respect to how much time interviews will involve. All interviews will be digitally recorded when possible; digital files will be stored on a password-secured network drive. Recordings will be transcribed verbatim and de-identified. Recordings will be destroyed at the end of the study.

PROTOCOL TITLE: Designing with Dissemination in Mind: Optimization of a mHealth Physical Activity Intervention for Breast Cancer Survivors (Fit2Thrive)

All raw data will be de-identified and kept confidential. Electronic versions of all data will be kept on a password protected network with access limited to study investigators. Only the investigators will have access to participant data. Confidentiality will be further maintained by reporting only group level data in study publications and presentations. All staff with access to the data will have completed Northwestern University requirements for the responsible conduct of research including the Collaborative Institutional Training Initiative (CITI) Training Modules.

9.4 Study Measures.

A. Phase 1

Interviews

- Questions for the interviews are included in the Appendix. Questions will be related to their perceptions of specific intervention/app components, recommendations for features, changes or enhancements.

App Development Session 1 Survey

- This survey asks participants about their preferences and opinions regarding app features to assist in app development and design. Participants will also provide opinions on images/wireframes of potential app features.

Post-Field Test Survey for Individuals Given the App to Test:

- Participants will provide information on:
 - Learnability: Ease and time to learn system
 - Effectiveness: System's ability to promote performance and productivity
 - Efficiency: System's ability to improve speed at which they perform
 - Errors: Impact of errors on using system and ability to recover from errors
 - Flexibility: System's ability to provide different command or routes to achieve same goal
 - Memorability: Ability to remember how to use system next time and ability to re-learn system after periods of non-use
 - User Satisfaction: Fondness, perceptions and opinion of system and its features

App Notifications Field Test Survey (Wave 2 Field Test)

- Participants will be asked to rate app notification message content and provide any additional feedback for improving messages.

B. Phase 2

Primary Outcome Measures

Feasibility: This will be measured during the intervention, immediately post-intervention and after the follow-up period. Measures include:

- *Intervention reach:* # of participants enrolled/# of eligible individuals

PROTOCOL TITLE: Designing with Dissemination in Mind: Optimization of a mHealth Physical Activity Intervention for Breast Cancer Survivors (Fit2Thrive)

- Participant retention: # of participants who drop out/# of participants randomized
- *Intervention Adherence*: % of weeks adhered to exercise prescription during intervention period
- *Intervention Maintenance*: % of weeks adhered to exercise prescription during follow-up period
- *Intervention component engagement*:
 - During intervention: # of times, on average, participants interacted with each intervention component during intervention
 - During follow-up: # of times, on average, participants interacted with each intervention component during follow-up
 - Total: # of times, on average, participants interacted with each intervention component over intervention and follow-up

Acceptability: This will be measured via a process evaluation immediately post-intervention and after the follow-up period. This evaluation will assess the following:

- perceived effectiveness of intervention components/app; use of app/intervention materials; plans to continue PA/app use; elements of intervention liked/disliked; satisfaction with program delivery, assessments and staff

Screening

Physical Activity Readiness Questionnaire (PAR-Q)⁹⁶ This pre-screening questionnaire assesses cardiovascular disease history, symptoms, risk factors and other health issues. Women indicating ≥ 1 positive statements will be required to obtain medical clearance from their primary care physician or oncologist.

Other Measures

All measures will be used for both breast cancer survivor participants and buddies unless otherwise indicated. Assessment will be conducted at baseline, 3 weeks (survivors only), 12 weeks and 24 weeks.

Mobile Device Proficiency Questionnaire⁹⁸ This survey assess both assessing both basic and advanced proficiencies related to smartphone and tablet use across eight subscales: (a) Mobile Device Basics, (b) Communication, (c) Data and File Storage, (d) Internet, (e) Calendar, (f) Entertainment, (g) Privacy, and (h) Troubleshooting and Software Management.

Demographics. Data will be collected on participant's current age, race, ethnicity, employment status, number of children, education, marital status, income, height and weight.

Breast Cancer History. Participants will be asked to indicate their current menopausal status and provide details on the prior breast cancer diagnosis including: date of diagnosis, stage of disease, treatment type and duration and hormone receptor status. Women will be asked to indicate similar data for any cancer recurrences or second

PROTOCOL TITLE: Designing with Dissemination in Mind: Optimization of a mHealth Physical Activity Intervention for Breast Cancer Survivors (Fit2Thrive)

cancer diagnoses. **This measure will only be used for breast cancer survivor participants.**

Health History. Participants will be asked to rate their general, overall health status, indicate whether they have been diagnosed with a list of 20 chronic conditions including diabetes, heart disease, multiple sclerosis, depression, etc. and provide information of other general health behaviors (e.g. smoking, drinking, fruit and vegetable consumption, etc.). **A slightly different version to capture potential cancer diagnoses will be used for buddy participants.**

*Godin Leisure Time Exercise Questionnaire (GLTEQ).*⁹⁹ The GLTEQ is a simple, self-administered instrument that has been widely used in epidemiological, clinical, and behavioral change studies and has been shown to be both a valid and reliable measure of PA participation. Participants will be asked indicate the frequency and average amount of time they spent engaging in strenuous (e.g., jogging), moderate (e.g., fast walking), and mild (e.g., easy walking) exercise over the past seven days. Weekly frequencies of strenuous, moderate, and light activities are multiplied by nine, five, and three, respectively. These values are added to obtain a total leisure activity score. Test-retest reliability coefficient range from $r=0.48$ for light and moderate activity to 0.94 for strenuous. For total values the test-retest reliability coefficient is 0.74.⁹⁹ **Breast cancer survivors will also answer a modified version asking them about their PA before diagnosis at baseline.**

Actigraph Accelerometer (model wGT3X-BT, Health One Technology, Fort Walton Beach, FL). The Actigraph is a valid and reliable objective PA measure.^{100,101} It is small, lightweight, has a rechargeable battery that lasts for up to 25 days and provides no feedback to participants. Participants will be instructed to wear the monitor on the non-dominant hip during all waking hours for 7 consecutive days, except when bathing or swimming. Activity data will be collected in one-minute intervals (epochs). Participants will record any time the accelerometer was not worn on a log. The ActiLife software will be used to derive wear time, identify outliers and summarize daily variables of the minute-by-minute data. Non-wear time will be defined as intervals of at least 60 consecutive minutes of zero counts, with allowance for up to 2 minutes of observations of less than 100 counts/min within the non-wear interval.¹⁰² A valid day of accelerometer wear will be defined as ≥ 10 hours of wear time. Each valid minute of wear time will be classified according to intensity (counts/min) using commonly accepted activity count cut-points^{102,103} as follows: sedentary (<100), light activity (100-759), lifestyle activity (760-2019), and MVPA (≥ 2020). **This measure will only be used for breast cancer survivor participants.**

*Sitting Time Questionnaire.*¹⁰⁴ Women will be asked to indicate the amount of time they spend on a typical weekday and weekend sitting in the following activities: traveling to and from places, while at work, while watching television, while using a computer at home in leisure time NOT including television (e.g. visiting friends, movies, dining out, etc.). Test-retest reliability coefficients were high for weekday sitting time at work,

PROTOCOL TITLE: Designing with Dissemination in Mind: Optimization of a mHealth Physical Activity Intervention for Breast Cancer Survivors (Fit2Thrive)

watching television and using a computer at home ($r_s=0.78-0.84$) but are more variable for weekend days across all domains ($r_s=0.23-0.74$).¹⁰⁴

PROMIS Applied Cognition-General Concerns Short Form 8a.¹⁰⁵ The PROMIS Applied Cognition General Concerns Short Form 8a will be used to assess participants' frequency of perceived cognitive function over the past 7 days ranging from 1 (not at all) to 5 (very often). Higher scores reflect higher levels of cognitive concerns. The reliability of this measure ranges from $\alpha=0.90$ to $\alpha=0.95$.¹⁰⁶

PROMIS Physical Function Short Form 20a.¹⁰⁵ The PROMIS Physical Function Short Form 20a will be used to assess participants' physical function. The scale has two subscale limitations and interference. For the 6 limitations items, participants will rate the level of difficulty they have had executing discrete activities over the past 7 days on a scale from 1 (unable to do) to 5 (without any difficulty). For the 4 limitations items, patients will rate the degree to which their health limits them in specific activities on a scale from 1 (cannot do) to 5 (not at all). Higher scores reflect better physical function. The reliability of this measure ranges from $\alpha=0.90$ to $\alpha=0.95$.¹⁰⁶

PROMIS Fatigue Short Form 8a.¹⁰⁵ The PROMIS Fatigue Short Form 8a will be used to assess participants' frequency of fatigue symptoms ranging from 1 (not at all) to 5 (very much) and fatigue interference ranging from 1 (never) to 5 (always) over the past 7 days. Higher scores reflect higher levels of fatigue. The reliability of this measure ranges from $\alpha=0.90$ to $\alpha=0.95$.¹⁰⁶

PROMIS Sleep Disturbance Short Form 8a.¹⁰⁵ The PROMIS Sleep Disturbance Short Form 8a will be used to assess participants' rating of overall sleep quality from 1 (very good) to 5 (very poor) and perceptions of specific characteristics of sleep quality on a scale ranging from 1 (not at all) to 5 (very much). Higher scores reflect higher levels of sleep disturbance. The reliability of this measure ranges from $\alpha=0.90$ to $\alpha=0.95$.¹⁰⁶

PROMIS Depression Short Form 8a.¹⁰⁵ Participants are asked to indicate the frequency of a variety of depressive symptoms over the past 7 days on a 5 point scale from 1 (never) to 5 (always). Higher scores reflect higher depressive symptoms. The reliability of this measure ranges from $\alpha=0.90$ to $\alpha=0.95$.¹⁰⁶

PROMIS Sleep-Related Impairment Short Form 8a.¹⁰⁵ The PROMIS Sleep –Related Impairment Disturbance Short Form 8a will be used to assess participants' perceptions or sleep-related impairment on a scale ranging from 1 (not at all) to 5 (very much). Higher scores reflect higher levels of sleep-related impairment. The reliability of this measure ranges from $\alpha=0.90$ to $\alpha=0.95$.¹⁰⁶

Physical Activity Neighborhood Environment Survey.¹⁰⁷ Participants are asked to indicate the different facilities and features of the area around their home that they could walk or bike. The items on this measure have demonstrated test-retest interclass correlations ranging from 0.52 to 0.88 and spearman correlations between single items

PROTOCOL TITLE: Designing with Dissemination in Mind: Optimization of a mHealth Physical Activity Intervention for Breast Cancer Survivors (Fit2Thrive)

and similar subscales from a more detailed measure were significant and ranged from 0.27 to 0.81.¹⁰⁷

*Exercise Self-efficacy Scale.*¹⁰⁸ The 6-item Exercise Self-Efficacy Scale will be used to assess participants' beliefs in their ability to exercise five times per week, at a moderate intensity, for 30 or more minutes per session at two week increments over the next 12 weeks. Items will be rated on a 100-point percentage scale with 10-point increments, ranging from 0% (not at all confident) to 100% (highly confident). The internal consistency for this measure has demonstrated acceptability ($\alpha=0.90$).¹⁰⁸

*Barriers Self-efficacy Scale.*¹⁰⁸ The 15-item Barriers Self-Efficacy Scale will be used to assess participants' beliefs in their ability to exercise three times per week for the next 3 months in the face of commonly experienced barriers to activity. Items will be rated on a 100-point percentage scale with 10-point increments, ranging from 0% (not at all confident) to 100% (highly confident). The internal consistency for this measure has demonstrated acceptability ($\alpha=0.86$).¹⁰⁸

*Social Support for Exercise Scale.*¹⁰⁹ This scale assesses the degree to which friends and family have demonstrated support for exercise behaviors in the previous 3 months. The frequency for each item is rated once for both family and friends on a 5-point Likert scale, ranging from 1 (never) to 5 (very often). The friend and family subscales have demonstrated acceptable internal consistency ($\alpha=0.84$ and $\alpha=0.84$, respectively).¹⁰⁹

*Effective Social Support for Physical Activity.*¹¹⁰ This scale assesses perceptions of support given (for buddy) and received (for BCS). The scale assesses three different types of help or support: 1) Help with practical needs, 2) Advice or information, and 3) Emotional support. **There will be a separate version for Buddies and breast cancer survivor participants assigned to the buddy condition only.**

*Exercise Goal-setting Scale.*¹¹¹ This 10-item scale will assess participants exercise-related goal-setting, self-monitoring and problem solving and instructs participants to indicate the extent to which each of the statements describes them on a scale from 1 (does not describe) to 6 (describes completely). This scale has demonstrated good internal consistency ($\alpha= 0.89$).¹¹¹

*Multidimensional Outcome Expectations for Exercise Scale.*¹¹² This scale will assess participants' social (4 items), self-evaluative (5 items), and physical (6 items) outcome expectations for exercise participation on a 5 point scale ranging from 1 (strongly disagree) to 5 (strongly agree). The three subscales have demonstrated good internal consistency ($\alpha= 0.82$ for physical outcome expectations, $\alpha= 0.81$ for social outcome expectations, and $\alpha= 0.84$ for self-evaluative outcome expectations).¹¹²

*Physical Activity Enjoyment Scale.*¹¹³ This 18-item scale will assess the degree to which participants, at the current moment, enjoy doing any sort of physical activity. This 18-item scale rates enjoyment on a 7-point bipolar scale ("It makes me depressed"..."It makes me happy"). This measure has demonstrated good internal consistency in previous studies ($\alpha= 0.93$ to $\alpha= 0.96$).¹¹³

PROTOCOL TITLE: Designing with Dissemination in Mind: Optimization of a mHealth Physical Activity Intervention for Breast Cancer Survivors (Fit2Thrive)

Table 6. Schedule of Measures					
	Screening	Baseline	3 weeks	12 weeks	24 weeks
Physical Activity Readiness Questionnaire	X				
Mobile Device Proficiency Questionnaire		X			
Demographics		X			
Breast Cancer History		X		X	X
Health History		X		X	X
Actigraph Accelerometer		X		X	X
Godin Leisure Time Exercise Questionnaire-Current		X	X	X	X
Godin Leisure Time Exercise Questionnaire-Before diagnosis		X			
Sitting Time Questionnaire		X		X	X
PROMIS Physical Function Short Form 20a		X		X	X
PROMIS Fatigue Short Form 8a		X		X	X
PROMIS Depression Short Form 8a		X		X	X
PROMIS Anxiety Short Form 8a		X		X	X
PROMIS Emotional Support Short Form 8a		X		X	X
PROMIS Sleep Disturbance Short Form 8a		X		X	X
PROMIS Sleep-Related Impairment Short Form 8a		X		X	X
Rosenberg Self-Esteem Scale		X		X	X
Physical Self-Perception Profile Physical Self-worth Subscale		X		X	X
Physical Activity Neighborhood Environment Survey		X			
Exercise Self-efficacy Scale		X	X	X	X
Barriers Self-efficacy Scale		X	X	X	X
Social Support for Exercise Scale		X	X	X	X
Effective Social Support for Physical Activity		X	X	X	X
Exercise Goal-setting Scale		X	X	X	X

PROTOCOL TITLE: Designing with Dissemination in Mind: Optimization of a mHealth Physical Activity Intervention for Breast Cancer Survivors (Fit2Thrive)

Physical Activity Enjoyment Scale		X	X	X	X
Multidimensional Outcome Expectations for Exercise Scale		X	X	X	X
Post-Program Evaluation				X	X
*Values in bold indicate BOTH survivors and buddies will be asked to complete measure at a given time point. Italics indicate only survivors in buddy condition and buddies will complete.					

Post-intervention Interviews. Questions for the interviews are included in the Appendix. Questions will be related to their perceptions and opinions of the intervention, overall, and specific intervention/app components and recommendations for improving the intervention in the future.

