Events may also be spontaneously reported to staff during contact time. Adverse events and serious adverse events may also be identified during regularly scheduled calls or emails by researchers blinded to the treatment condition of the participant. These phone interviews or emails will be conducted every 8 weeks throughout the 24 week study period. Breast cancer survivors participants will be asked to complete the Non-spontaneous Adverse Events Questionnaire either via RedCap or via an interview with study staff. This form will be completed for all breast cancer survivor participants and will query the participant as to whether they have had any health and/or medical problems during the preceding 8 week period. Participants will be called or emailed until a response is received. Participants will also be required to provide the investigators with at least one emergency contact to have on file in the event we are fail to reach the participant after 5 or more attempts. If participant reports "YES" to item 5A-5D (see RedCap form), an adverse event form will be filed with the IRB. The non-spontaneous Adverse Events Questionnaire will not be given to buddies of BCS participants to complete since they are not being specifically asked or encouraged to increase their physical activity participation.

All identified adverse events will be reported to the PI and recorded and reported in an adverse event log (includes subject's name, date and event description). The PI will consult with co-investigators, the IRB and NU Office for the Protection of Research Subjects to determine whether the event should be classified as 'non-attributable', 'possibly attributable' or 'attributable' to the current project and 'serious' or 'non-serious.' Adverse event reports will be submitted to the IRB within 5 business days of the event or notification to the PI that the event has occurred. All serious adverse events will be reported to the RHLCCC Clinical Research Office for review by the Data Monitoring

PROTOCOL TITLE: Designing with Dissemination in Mind: Optimization of a mHealth Physical Activity Intervention for Breast Cancer Survivors (Fit2Thrive)

Committee, IRB, and the National Cancer Institute, as applicable, using appropriate forms. Any action to be taken will be recorded in the adverse event log.

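### The adverse event definition in 9.2 is the test for an unanticipated problem; it does not fit the protocol's own attribution classes and, read literally, keeps foreseeable non-serious exercise injuries out of the log and the semi-annual list

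*Combined protocol and SAP*

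**What the plan says.** All the relevant rules sit in section 9.2, under Monitoring subjects for safety for Phase 2.

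- **Definition.** An adverse event "is defined as an unanticipated problem which meets all of the following criteria: a) unexpected (in terms of nature, severity, or frequency"). The second criterion is relatedness: "b) related or possibly related to participation in the research". Under the third criterion, (c), an event counts only if it "suggests that the research places subjects or others at a different or greater risk of harm than was previously known or recognized". All three must hold.
- **Log and attribution.** "All identified adverse events will be reported to the PI and recorded and reported in an adverse event log". After consulting the co-investigators, the IRB and the research-protection office, the principal investigator decides whether the event is to be "classified as 'non-attributable', 'possibly attributable' or 'attributable' to the current project", and whether it is serious.
- **Seriousness.** A serious "adverse event is defined as any event in which the outcome results in any of the following", followed by a list of outcomes that includes inpatient hospitalisation. "All other events will be considered 'non-serious".
- **Reports.** "Adverse event reports will be submitted to the IRB within 5 business days of the event or notification to the PI" of it. Separately, a YES to items 5A-5D of the 8-weekly questionnaire triggers an adverse event form to the IRB, and a later sentence mentions reporting any events to the IRB. Non-serious adverse events go to the Clinical Research Office twice a year. The semi-annual progress report to the Data Monitoring Committee includes reported adverse events.

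Section 14.1 (Phase 2) names muscle soreness, strains and aggravated arthritis as foreseeable risks of starting activity after a sedentary period. Sections 8.2 and 12.0 are marked N/A, so no other section defines an adverse event. Section 9.3 applies the Phase 2 procedures to the Phase 1 field test, so the same definition governs there.

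**The concern.** The term *adverse event* decides what enters the log, what goes on the semi-annual non-serious list and what the Data Monitoring Committee sees counted. Here relatedness, unexpectedness and raised risk are conditions for entry, whereas the attribution step in the same section treats relatedness as something judged about an event already called an adverse event.

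In a physical activity trial in inactive survivors, the harms the protocol itself anticipates are minor exercise injuries. A definition that requires an event to be unexpected screens out those harms when they occur as foreseen. It also weakens criterion (a) on its own terms. That criterion counts unexpected frequency, but if expected injuries are not logged, the log holds no running count in which an excess could be noticed.

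Section 11.1 (Aim 3) says that missing certain safety benchmarks would lead to refinement of the protocol. A safety benchmark needs a stable definition of the event being counted.

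**Working it through.** No arithmetic applies, and the plan gives no figure to reproduce. The check sets the rules side by side and runs hypothetical events through them.

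**Step 1: apply the three criteria.** The event types below are illustrative; the foreseeable injuries are those of section 14.1.

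| Event | (a) unexpected | (b) related | (c) raised risk | Adverse event? |
|---|---|---|---|---|
| Soreness, strain or aggravated arthritis from the programme, of expected severity and frequency | no | yes | no | no |
| The same injury, worse or more frequent than expected | yes | yes | must be judged | only if (c) is met |
| Unrelated non-serious illness | either | no | not needed | no |
| Unrelated hospitalisation | either | no | not needed | no under the three criteria; see Step 3 |
| Related but expected hospitalisation | no | yes | not needed | no under the three criteria; see Step 3 |

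**Step 2: compare with the attribution classes.** The events to be classified are logged adverse events. One class is non-attributable, but criterion (b) requires at least possible relatedness. An event placed in that class therefore fails the definition that admitted it. The section does not say whether the entry stays in the log, is removed, or still counts in the semi-annual list.

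**Step 3: compare with the seriousness sentences.** There are two readings.

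- *Stand-alone.* Any event with a listed outcome is a serious adverse event, whatever its cause. Both hospitalisations in the table are then serious adverse events without meeting the definition of an adverse event.
- *Inherited.* Any event means any such event, so the three criteria carry over. The section is then consistent on this point, but unrelated or expected hospitalisations are not serious adverse events and fall outside serious reporting.

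The text does not choose between them.

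**Step 4: follow the rows marked no through the reports.**

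- *Adverse event log:* limited to adverse events. Foreseeable injuries as expected and unrelated non-serious events are outside it.
- *Semi-annual non-serious list:* also limited to adverse events, with the same result.
- *Data Monitoring Committee report:* covers reported adverse events. The events may be missing, but the phrase could also take in anything filed on an IRB form.
- *IRB:* undetermined. Items 5A-5D are not reproduced in the documents, and the remark about reporting any events is wider than the definition.

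**Step 5: check data collection.** Every 8 weeks over the 24-week study, the questionnaire asks survivors about any health or medical problem. The gap is therefore in classification and reporting, not in collection.

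**The case against.** The best reply is that section 9.2 describes a sequence. Any staff member may identify an event, it is logged provisionally, and attribution is settled afterwards by consultation. On that reading *non-attributable* is simply the outcome for an event found to be unrelated, and the class has members. This reading is available, so a reader who infers that the class can never be used goes further than the text. What remains is that the protocol does not call the first entry provisional and does not say what becomes of an event found unrelated. Nor does the sequence help the foreseeable injuries: they fail on expectedness and raised risk, and the classification step covers only attribution and seriousness.

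A second reply is that the serious and non-serious sentences subdivide the term just defined. That is a fair reading, so a reader should not infer that the section flatly contradicts itself on seriousness. It is an ambiguity. The coherent reading has its own price, since unrelated or expected hospitalisations then leave serious reporting.

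A third reply is that some injuries may reach the IRB, and through it the Data Monitoring Committee counts, via items 5A-5D. This stands. The documents do not support the inference that every safety report omits these events.

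Finally, the study is classed as minimal risk and the health data are collected in any case. That limits the consequence but leaves the definition as it is.

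**Conclusion.** The concern holds within limits. Section 9.2 uses the test for an unanticipated problem as its definition of an adverse event, and this is inconsistent with its own attribution scheme. Taken literally, foreseeable exercise injuries of expected severity and frequency, and unrelated non-serious events, fall outside the log and the semi-annual non-serious list. Their absence from the Data Monitoring Committee counts is possible but not established, and whether they reach the IRB cannot be settled from the documents.

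The treatment of serious events depends on which reading of the seriousness sentences is used. Injuries worse or more frequent than expected can still qualify if they also meet (b) and (c).

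The size in events cannot be computed, because the documents give no expected event rate. Adverse events are not among the study endpoints in section 8, so the feasibility endpoints and the component-effect estimates are untouched. The conclusion rests on reading the definition as written and on no other section supplying one. It should be corrected because the wording is a stated rule that staff would follow, not merely a missing detail.

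**What to change.** Reconcile the definition with the logging, attribution and reporting rules of section 9.2 in one amendment:

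1. Use a single adverse event definition for the log and the semi-annual reports, with relatedness and expectedness recorded as attributes rather than entry conditions. All three attribution classes can then be used.
2. Label the three-criterion test as the definition of an unanticipated problem.
3. Make the serious and non-serious sentences refer to the single adverse event definition.
4. State which events fall under the 5-business-day IRB rule: unanticipated problems, a YES to items 5A-5D, or all adverse events.
5. State which definition the Data Monitoring Committee counts use.

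The cost is protocol wording and attribute fields in the existing log, with no new data collection. The drawback is more log entries and more attribution decisions, each of which currently goes through consultation with the co-investigators, the IRB and the research-protection office. The added IRB workload depends on item 4, so that rule should be rewritten at the same time.
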